(1) Resuscitation requiring early intubation according to the American Academy of Pediatrics guidelines for neonatal resuscitation [8]; (2)major congenital malformations or known complex congenital heart disease; (3)pulmonary hemorrhage or pneumothorax; (4) congenital lung diseases or malformations or pulmonary hypoplasia;

Setting

We plan to enroll preterm infants born between 26 and 34 weeks of gestational age from 18 tertiary NICUs in China. These 18 tertiary NICUs have more than 800 NICU beds and annual admissions of nearly 8,000 preterm infants with RDS each year. The first (XZ) and last authors (RR) take responsibility for the accuracy and completeness

of the trial.

Randomization

To avoid the chance of having more infants in one group than another, block randomization will be applied, with a block size of 4. The envelopes are sealed, shuffled, and then numbered in sequential order from 1 to 4. A clinician who is not in the trial group will open the envelope and randomize patients. This procedure will be repeated for each group of four infants. Infants will be stratified according to 26^{0/7}-27^{6/7} weeks, 28^{0/7}-29^{6/7} weeks, 30^{0/7}-31^{6/7} weeks and 32^{0/7}-33^{6/7} weeks. Infants born from multiple gestations will be assigned by individual randomization. Infants randomized to one arm cannot crossover to the other or vice-versa during the study.

Trial intervention

Ventilators

CPAP: CPAP will be provided by continuous flow devices (CNO Medin, Germany or Carefusion, USA) Bubble CPAP devices will not be used.

NHFOV: NHFOV will be provided by two ventilators (CNO, Medin, Germany or SLE 5000, UK). The Medin CNC ventilator produces high-frequency oscillations by flow interruption with cyclic opening-closure of the end expiratory valve. Otherwise, The SLE 5000 ventilator is a time-cycled, pressure-limited and continuous-flow neonatal ventilator.

Before the beginning of the study all ventilators will be checked to ensure that there is no malfunction.

Interfaces

CPAP and NHFOV will be all administered through short, low-resistance binasal prongs,

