The primary outcome of this trial will be to determine the need for IMV in the first 7 days of life in preterm infants randomized to the two groups. Secondary outcomes include days of hospitalization, days on noninvasive ventilation, days on supplemental oxygen, pre-discharge mortality, surfactant doses, incidence of stage III ROP and BPD, occurrences of abdominal distention, air leaks, IVH \geq grade 3 and NEC. Secondary outcomes also include Bayley Scales of Infant Development at 18-24 months of corrected age. BPD will be defined according to the National Institutes of Health consensus definition as mild, moderate and severe BPD [12], IVH classification according to Papile et al [13] and for NEC, Bell staging will be used [14].

Data collection

Patient demographic data include: sex, birth weight, gestational age, Apgar scores, mode of

delivery, prenatal corticosteroid use, premature rupture of the membrane, RDS Silverman score and critical risk index for babies-II (CRIB-II) score. More details see in the appendix Clinical data :Including the need for IMV, days of hospitalization, days on noninvasive respiratory support, days on supplemental oxygen, mortality, the need for surfactant, occurrences of abdominal distention, air leaks, IVH \geq grade and NEC \geq stage II. More details see in the appendix Follow-up data: The incidence of BPD and ROP at a post-menstrual age of 36 weeks or at discharge, and Bayley Scales of Infant Development at 18-24 months of corrected age.

Sample size calculation

It is difficult to calculate a sample size for such a study, since it is the first to investigate NHFOV vs CPAP in primary support phase in preterm infants with RDS. There is only one preliminary study available about the primary outcome “need for IMV”. This pilot study conducted by Zhu et al provides data about the primary outcome “need for IMV”. This trial showed the need for IMV was significantly lower in the NHFOV compared with the NCPAP group (24.3% vs. 56.4%, $P < 0.01$). Considering an α -error of 0.05 and a power of 90%, 150 neonates should be enrolled in each arm (with a 1:1 design) to detect the same difference.

Statistical methods

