Data will be analyzed using SPSS version 19 software. The statistical analyses include Student's t-test for continuous data and compared proportions using Chi-squared test, and Fisher's exact test for categorical data. Predefined four subgroups are 26^{0/7}-27^{6/7} weeks, 28^{0/7}-29^{6/7} weeks, 30^{0/7}-31^{6/7} weeks and 32^{0/7}-33^{6/7} weeks, and subgroup analyses will be conducted for the primary outcome in the preterm infants. To further evaluate the effect of NHFOV on intubation within

subgroup, the test of treatment-by-gestational age subgroup interaction will also be done using the paired binary logistic regression. For the preterm infants lost to follow-up, the missing values of the primary and secondary outcomes are replaced using multiple imputation. A P -value < 0.05 will be regarded as statistically significant.

Data Safety Monitoring Board (DSMB): [name], Professor of Pediatrics, Oklahoma University Medical Center, Oklahoma, [name], Professor of Pediatrics, Medical College of Georgia, Georgia Health Sciences University, Augusta, Georgia, and [name], MD., MPH (Biostatistics and Epidemiology) Assistant Professor of Pediatrics, Keck School of Medicine of the University of Southern California, Los Angeles, California will serve as DSMB members. [name] will also serve as consultant for statistical analysis.

Registration number

The trial has been approved by the centralized ethics committee (The Ethics Committee of Daping Hospital, Research Institute of Surgery, Third Military Medical University) and registered at <http://www.clinicaltrials.gov>(ID: NCT03099694).

Discussion

In the past decades, several clinical trials have compared the effects between NHFOV and NCPAP in neonates as a rescue mode or during weaning from IMV. These trials demonstrated that NHFOV applied with nasopharyngeal tube are more beneficial than NCPAP in reducing CO₂ levels [16-19]. Recently, two retrospective case series also reported NHFOV could be applied in preterm infants as a rescue treatment after the

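### The gestational-age interaction test is named as a paired logistic regression, but the trial is unpaired and no pair is defined (minor; wording to correct)

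*Combined protocol and SAP*

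**What the plan says.** The Statistical methods section defines four gestational-age (GA) subgroups and says that "subgroup analyses will be conducted for the primary outcome in the preterm infants". It then adds that "the test of treatment-by-gestational age subgroup interaction will also be done using the paired binary logistic regression". This is the only mention of pairing in the document.

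The other methods in that section are for independent groups: Student's t-test for "continuous data and compared proportions using Chi-squared test", and Fisher's exact test.

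The Randomization section says that "block randomization will be applied, with a block size of 4", with stratification by the same four GA bands. It also says: "Infants born from multiple gestations will be assigned by individual randomization". And: "Infants randomized to one arm cannot crossover to the other or vice-versa during the study".

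The Sample size calculation section concludes that "150 neonates should be enrolled in each arm (with a 1:1 design) to detect the same difference", from overall rates of 24.3% (NHFOV) and 56.4% (NCPAP). It gives no rates by GA band.

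**The concern.** A paired binary logistic regression, in its usual sense of conditional logistic regression on matched pairs, needs each NHFOV infant to be linked to a particular NCPAP infant. Nothing in the plan makes that link. The sentence also leaves out the model terms and the degrees of freedom, so nothing nearby shows what the adjective was meant to convey. It could stand for ordinary regression, for pairwise comparisons between strata, or for a matching that was never described.

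What is at stake is limited but real. This is the only interaction test planned across the GA subgroups, so it would bear on any statement that the effect of NHFOV differs by gestational age. A prespecified test should not leave the analyst to choose among readings once outcomes are known.

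**Working it through.** **Step 1. Could the design supply pairs?** Each possible source, set against the text:

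- *Within-infant pairs:* excluded, because crossover is not allowed.
- *Siblings:* randomised individually, so they may fall in the same arm, and singletons have no partner.
- *Blocks:* a block of four does not say which infant goes with which.
- *GA strata:* these are the levels of the effect modifier under test, not pairs.
- *A matching variable:* none is given in the main text or in the appendix definitions.

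The plan gives no numerical figure for this test, so there is none to reproduce. Steps 2 to 4 apply only to the literal reading.

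**Step 2. How much would a 1:1 conditional model discard?** Only discordant pairs contribute. Inputs from the Sample size calculation section: p(NHFOV) = 0.243, p(NCPAP) = 0.564, 150 per arm. If paired infants are independent at these rates:

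- event in the NHFOV infant only: 0.243 × (1 − 0.564) = 0.243 × 0.436 = 0.106
- event in the NCPAP infant only: 0.564 × (1 − 0.243) = 0.564 × 0.757 = 0.427
- discordant share: 0.106 + 0.427 = 0.533

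So about 0.533 × 150 = 80 pairs are informative and 70 (47%) are dropped, which is 140 of 300 infants. The ordinary model uses all 300.

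**Step 3. Does the p-value depend on the pairing?** This illustration uses assumed data, since the documents give no stratum sizes or risks.

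| Stratum | Infants per arm | NCPAP events | NHFOV events | Odds ratio |
|---|---|---|---|---|
| 1 | 38 | 27 | 6 | (6×11)/(32×27) = 0.08 |
| 2 | 38 | 23 | 8 | (8×15)/(30×23) = 0.17 |
| 3 | 37 | 19 | 9 | (9×18)/(28×19) = 0.30 |
| 4 | 37 | 15 | 13 | (13×22)/(24×15) = 0.79 |
| Total | 150 | 84 (56.0%) | 36 (24.0%) | |

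- *Ordinary model:* likelihood-ratio test of treatment + stratum against treatment + stratum + product, 3 df. Chi-squared = 11.12, p = 0.011.
- *Paired model:* with b and c discordant pairs of each kind in a stratum, test whether b/(b + c) is equal across the four strata (likelihood ratio, 3 df). Over 20,000 random within-stratum pairings, the 2.5th, 50th and 97.5th percentiles of p were 0.0008, 0.023 and 0.144, and 24% were at 0.05 or above. On average about 82 of the 150 pairs were informative.

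The gradient here is steep, roughly tenfold in odds ratio (0.79/0.08), and was chosen to show the dependence. It is not a typical case.

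**Step 4. What would pairing do to power?** Simulation of 20,000 trials per scenario, with the same assumed stratum sizes, overall rates fixed at 56.4% and 24.3%, control risk flat at 56.4%, odds ratios log-linear across strata, and nominal 5% tests:

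| Ratio of odds ratios, extreme strata | Ordinary | Paired |
|---|---|---|
| 1 (no interaction) | 5.5% | 6.9% |
| 1.8 | 10.4% | 10.8% |
| 2.5 | 18.8% | 17.5% |
| 4 | 37.6% | 32.4% |
| 9 | 74.6% | 65.1% |

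The loss is nil at 1.8-fold and about 1, 5 and 9 to 10 points at 2.5-, 4- and 9-fold. Letting control risk fall across strata (75/62/50/38%) gave similar losses. The paired test rejects slightly more often with no interaction, so these comparisons are at nominal, not equal, size.

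**Step 5. The slip readings.** If ordinary regression was meant, the numerical effect is zero. If pairwise was meant, four strata give 4 × 3/2 = 6 contrasts. That is a different procedure from one joint test, and the section gives only a 0.05 threshold with no rule for multiple comparisons. No size has been worked out for that reading.

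**The case against.** The strongest reply is that one adjective is wrong and everything else in the sentence is usable: the GA subgroups, the interaction and binary logistic regression are all named. Most statisticians would read past the word and fit the ordinary model, with no effect on any number. The figures in steps 2 to 4 describe the least likely reading, and those in steps 3 and 4 rest on invented strata and gradients. Random pairing is also a construction of this review; a single rule fixed in advance would give a single p-value. All of this stands, and it is why the point is minor.

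A reader might infer that the test cannot be run as written. The documents do not support that. It can be run once someone forms pairs, as step 3 does. The defect is that the pairing is undefined and the method does not match the design.

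A reader might also infer that the primary result is at risk. It is not: the chi-squared or Fisher comparison of need for IMV does not use this model.

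What the reply does not remove is the ambiguity. The text does not say which reading was meant, and ordinary, pairwise and truly paired analyses are different tests.

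**Conclusion.** The point holds as a minor defect of specification. The plan attaches a paired method to an unpaired design and defines no pair. This rests on the text alone and is secure.

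Its practical size depends on the reading. It is zero if ordinary logistic regression was meant, which is a likely explanation. Under the literal reading, about half the pairs would be discarded at the protocol's overall rates, and the p-value would turn on an arbitrary choice. The spread of p-values and the power losses depend on assumed stratum sizes, risks and effects, so they show direction only and should not be read as a forecast for this trial.

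Only the secondary GA interaction test is affected. Correlation between siblings from multiple births is a separate matter: individual randomisation means that siblings are not pairs by design, but it does not make their outcomes independent. Neither the present wording nor the correction below deals with it.

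**What to change.** Replace the paired model with: ordinary (unpaired) binary logistic regression of need for IMV on treatment, GA stratum (four levels) and their product, with one joint 3-df test of the product terms as the interaction test. Because the section also says that "the missing values of the primary and secondary outcomes are replaced using multiple imputation", add that the joint test is pooled over imputations where imputation is used.

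If pairwise contrasts between strata were meant, report them only as descriptive follow-up to the joint test. If a real pairing was intended, define the pairing variable before the data are seen.

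The cost is one sentence of wording. No new data are needed, and the primary analysis does not change.

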**Noninvasive Ventilation for Preterm Neonates With
Respiratory Distress Syndrome: a Multi-center Randomized
Controlled Trial**

(NCT03099694)

13 July 2017

Solid PDF/A Express
<http://www.SolidDocuments.com/>

STUDY PROTOCOL

Noninvasive high-frequency oscillatory ventilation versus nasal continuous positive airway pressure in preterm infants with respiratory distress syndrome: Study protocol for a multi-center, prospective, randomized, controlled trial. For the Noninvasive High-Frequency Oscillatory Ventilation Study Group (NHFOV Study Group*).

Abstract

Background: Invasive mechanical ventilation is associated with development of adverse pulmonary and non-pulmonary outcomes in very low birth weight infants. Various modes of non-invasive respiratory support are being increasingly used to decrease the incidence of bronchopulmonary dysplasia (BPD). The aim of this trial is to compare the effect of noninvasive high-frequency oscillatory ventilation (NHFOV) and nasal continuous positive airway pressure (NCPAP) in preterm infants with respiratory distress syndrome (RDS) as a primary noninvasive ventilation support mode.

Methods/Design: In this multicenter, randomized, controlled trial, 300 preterm infants born at gestational age (GA) less than 34 weeks with a diagnosis of RDS will be randomized to NHFOV or NCPAP as a primary mode of noninvasive respiratory support. Study will be conducted in 18 tertiary neonatal intensive care units in China. The primary outcome is the need for invasive mechanical ventilation (IMV) during the first 7 days after enrollment in preterm infants randomized to the two groups. The

prespecified secondary outcomes include days of hospitalization, days on noninvasive respiratory support, days on IMV, days on supplemental oxygen, mortality, need for surfactant, severe retinopathy of prematurity(ROP) requiring laser or surgery, patent ductus arteriosus needing ligation, bronchopulmonary dysplasia(BPD), occurrence of abdominal distention, air leaksyndromes, intraventricular hemorrhage (IVH \geq grade 3), necrotizing enterocolitis (NEC \geq II stage) and nasal trauma. Other secondary outcomes include Bayley Scales of Infant Development at 18-24 months of corrected age.

Trial registration: ClinicalTrials.gov Identifier: NCT03099694.

Key words: Noninvasive high-frequency oscillatory ventilation; nasal continuous positive airway pressure; respiratory distress syndrome; preterm infants; surfactant; invasive mechanical ventilation

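### P<0.05 is the rule for every test, so claims from the 12 to 15 secondary outcomes have no controlled error rate, although the primary outcome keeps its 5%

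*Combined protocol and SAP*

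**What the plan says.** Statistical methods names the t-test, the chi-squared test and Fisher's exact test for continuous and categorical data in general, and closes with one criterion: "A P -value < 0.05 will be regarded as statistically significant". Nothing there ties the criterion to a particular outcome. The sentence just before it, on missing values, covers primary and secondary outcomes together. The same section plans analyses of the primary outcome in four gestational-age subgroups and a test of interaction between treatment and subgroup.

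There is one primary outcome. The Outcomes section states: "The primary outcome of this trial will be to determine the need for IMV in the first 7 days of life".

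The secondary outcomes are listed twice, and the lists differ:

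- **Abstract, Methods/Design.** The list begins: "prespecified secondary outcomes include days of hospitalization, days on noninvasive respiratory support, days on IMV, days on supplemental oxygen, mortality, need for surfactant". It goes on to severe retinopathy, ductal ligation, bronchopulmonary dysplasia (BPD), abdominal distention, air leak, intraventricular hemorrhage, necrotizing enterocolitis and nasal trauma, which makes 14. The Bayley scales are the fifteenth: "Other secondary outcomes include Bayley Scales of Infant Development at 18-24 months of corrected age".
- **Outcomes section.** This list has 12 items, again including the Bayley scales: "Secondary outcomes also include Bayley Scales of Infant Development at 18-24 months of corrected age". Days on IMV, ductal ligation and nasal trauma are not in it.

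No section defines a family of tests, a testing order, a split of alpha, an adjustment for multiplicity or an exploratory status for any of these analyses.

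**The concern.** Read as written, the plan lets each secondary outcome be declared significant at an unadjusted 5%. With 12 or more such tests on the same two arms, the chance that at least one is declared significant by chance alone is well above 5%. The error can run either way, as an apparent benefit or an apparent harm of NHFOV. The Abstract calls the main list prespecified, so a reader could take a significant secondary result for a planned, confirmed finding. BPD, air leak, retinopathy, intraventricular hemorrhage and necrotizing enterocolitis all fall in this group. The Discussion describes the trial as the first of its kind, so a chance finding would have no earlier multicenter trial to be weighed against.

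**Working it through.** The plan states no error rate for the secondary outcomes as a set, so there is no figure of its own to reproduce.

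**Inputs.** Alpha is 0.05 per test (Statistical methods). The number of secondary outcomes k is 15 (Abstract) or 12 (Outcomes). Three assumptions are added: tests are two-sided (the plan does not say), NHFOV affects no secondary outcome, and there is one test per outcome.

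**Step 1: expected false positives.** This is k × 0.05, whatever the correlation, if each test has its full 5% size.

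- k = 15: 15 × 0.05 = 0.75
- k = 12: 12 × 0.05 = 0.60

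**Step 2: chance of at least one, independent tests.** This is 1 − 0.95^k.

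- k = 15: 1 − 0.95^15 = 53.7%
- k = 12: 1 − 0.95^12 = 46.0%

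**Step 3: chance of at least one, correlated tests.** Hospital days, oxygen days, days on noninvasive support and BPD probably move together, so independence is the upper end. The documents give no correlation. The table comes from simulating k normal test statistics with a common correlation (200,000 runs per cell).

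| Correlation | k = 15 | k = 12 |
|---|---|---|
| 0 | 53.7% | 46.0% |
| 0.2 | 49.8% | 42.8% |
| 0.3 | 45.9% | 39.6% |
| 0.5 | 36.2% | 32.1% |
| 0.7 | 25.7% | 23.1% |

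**Step 4: conservatism of Fisher's exact test.** Suppose seven of the 15 outcomes are rare and tested this way: mortality, retinopathy, ductal ligation, air leak, intraventricular hemorrhage, necrotizing enterocolitis and nasal trauma. At 150 infants per arm and an assumed event rate of 1%, the true size of each test is 0.2%; at 10% it is 3.3%. With s for that size, the chance of at least one false positive among 15 independent tests is 1 − 0.95^8 × (1 − s)^7. This gives 35% at the 1% rate and 48% at the 10% rate. The event rates are assumptions. This effect was not combined with correlation; together they would lower the figures further.

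**Step 5: one direction only.** For a false claim favouring one given arm, alpha is 0.025 per test: 1 − 0.975^15 = 31.6% for 15 independent tests.

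**Step 6: subgroup and interaction tests.** Adding these five tests gives k = 20 and 1 − 0.95^20 = 64.2% under independence. That needs two further assumptions: no effect on the primary outcome either, and independence of an interaction test from the subgroup results it is built on. The figure is therefore not carried into the conclusion.

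**The case against.** The strongest case on the other side is that the trial's main inference is untouched. There is one primary outcome, the alpha in the sample size calculation belongs to it, and secondary tests do not inflate its error. This stands, and it limits the point to secondary and subgroup claims.

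It can also be said that the all-null scenario is artificial. If NHFOV changes need for IMV, days on IMV will change too. This stands as a caution: the percentages describe the rule under a stated scenario and do not predict this trial. Whether safety outcomes such as air leak and nasal trauma belong in one error-controlled family with efficacy outcomes is likewise a matter of judgement. The plan, however, makes no such distinction.

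Two stronger readings are tempting, and the documents support neither:

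- **That a false secondary claim is about as likely as not.** This needs the longer list of 15, tests that are independent or nearly so, full 5% size for every test and no true effect anywhere. The Outcomes section lists only 12 (46.0% even if independent), the outcomes are plausibly correlated, and Fisher's exact test is among the named methods.
- **That the trial's guideline aim rests on these tests.** The Discussion ties that aim first to reducing need for IMV, the primary outcome, and only then to morbidities that accompany IMV. The wording is hedged and commits to no analysis.

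Some details push the other way. Abdominal distention is defined in Appendix A3 by circumference at two times, and BPD is graded in three levels, so there may be more tests than outcomes.

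**Conclusion.** The point holds as a gap in control of secondary claims. The plan applies P<0.05 to every test, with no family, hierarchy or exploratory label. If NHFOV affected no secondary outcome, the chance of at least one falsely significant secondary result, in either direction, would be about 26–54% for the Abstract's 15 outcomes and about 23–46% for the 12 in the Outcomes section. The lower ends assume a correlation of 0.7 and the upper ends independence. Both assume two-sided tests at full 5% size, so use of Fisher's exact test on rare events would bring them down. Even the lower ends are between four and five times the nominal 5% or slightly above (23.1/5 = 4.6; 25.7/5 = 5.1). The mismatch between the two lists is a separate defect, but it means the number of tests is not fixed. The conclusion on need for IMV is not at risk, so this is a cheap improvement and not a threat to the trial.

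**What to change.** Replace the closing sentence of Statistical methods with:

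> Two-sided P<0.05 is applied to the primary outcome comparison in all randomized infants only. Secondary outcomes, gestational-age subgroup analyses and the interaction test are exploratory; they are reported as effect estimates (risk or mean differences, or odds ratios for the interaction) with 95% confidence intervals not adjusted for multiplicity, and no claim of statistical significance is made from them.

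Subgroup and interaction analyses need naming because they use the primary outcome and would otherwise have an unclear status. The words on all randomized infants separate the whole-trial comparison from the subgroups. They must also be squared with the exclusions after inclusion that Appendix A2 allows, which is a separate question.

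The cost is that secondary and subgroup results can no longer be called significant, and that effect estimates with intervals must be added to a section that now lists mainly hypothesis tests. No extra infants or data are needed and the primary test does not change. Possible harms stay visible through the intervals.

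If the sponsor wants a confirmatory secondary claim, a fixed testing order at 0.05 would serve. So would a Bonferroni threshold of 0.05/15 = 0.0033 or 0.05/12 = 0.0042, which holds the error for the set at 4.9% if the tests are independent. Either requires settling on one list first.
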